T_{1/2}	Terminal Half-life
TR	Test-Reference Sequence
ULN	Upper Limit of Normal
V_{ss}	Volume of Distribution at Steady State
WBC	White Blood Cells
WHO	World Health Organization
wk	Week(s)

1 STUDY RATIONALE

Lurbinectedin is a novel synthetic tetrahydroisoquinoline structurally related to ecteinascidins.

Lurbinectedin is a new chemical entity that binds the DNA leading to the formation of DNA double-strand breaks (DSBs). The binding to DNA is likely occurring in the minor groove region and induces apoptosis and delayed progression through the cellular phase S/G2. Lurbinectedin also induces the specific degradation of transcribing RNA Pol II in several human tumor cell lines.

In vitro, lurbinectedin demonstrated cytotoxic effects against a broad selection of tumor types with half maximal inhibitory concentration (IC₅₀) values in the range of 1-10 nM. Although selectivity was also seen, a clustering of sensitive tumors has not been identified. Lurbinectedin also exhibited antitumor activity against different murine models of xenografted human-derived tumor types. Lurbinectedin has been tested as a single agent or in combination with different drugs in solid tumors; while antitumor activity in hematological tumors was deemed negligible, lurbinectedin has shown activity in different solid tumors; some of the most responsive tumor types were breast, small cell lung cancer (SCLC), ovarian and endometrial cancer.

Based on current clinical data, the toxicity of lurbinectedin is predictable, reversible and manageable. The most relevant toxicity is reversible myelosuppression with a nadir occurring in the middle of the second week after Day 1 infusion in an every-three-week cycle; overall, the incidence of febrile neutropenia is below 20% in all ongoing Phase II trials.

Lurbinectedin is extensively metabolized by the cytochrome P450 enzymes, primarily CYP3A4. Thus, potent inducers or inhibitors of this enzyme may alter the plasma concentrations of lurbinectedin. This study is designed to examine the pharmacokinetics (PK) and safety of lurbinectedin when co-administered with bosentan, a moderate CYP3A4 inducer, in comparison with lurbinectedin alone. The results of this study may be used to support future clinical studies in patients and prescribing information in future labeling.

A full rationale for the study may be found in the appropriate sections of the study's clinical protocol.

2 OVERALL STUDY DESIGN

This is a prospective, open-label, two-way crossover, phase Ib drug-drug interaction study in patients with advanced solid tumors.

The study will include a pre-treatment (screening) phase (within 14 days before the first lurbinectedin or bosentan administration) followed by a treatment phase consisting of two lurbinectedin cycles, one cycle in combination with bosentan and one cycle of lurbinectedin as single agent (in different order depending on the study sequence), and one additional third cycle of lurbinectedin as a single agent for patients who meet the continuation criteria and obtain a clinical benefit after the first two cycles, and then follow-up of adverse events if any.

Patients who meet the continuation criteria and obtain a clinical benefit according to the Investigator's criteria will have the opportunity to continue treatment under a Compassionate Use Agreement after the completion of the optional third study cycle.

Patients will be treated as outpatients. At the discretion of the Investigator, patients may be admitted to the study center on Day -1 or Day 1 and monitored, at least, until completion of the Day 1 PK blood sample collections.

[figure not shown]
Patients will receive a maximum of three cycles: two consecutive cycles of lurbinecetin, one cycle with and one cycle without bosentan co-administration (in different order depending on the study Sequence 1 or Sequence 2 of treatment), followed by a third cycle with lurbinecetin alone (this last optional for patients with clinical benefit). Lurbinecetin will be administered as a 1-hour (-5/+20 min) i.v. infusion every three weeks (q3wk) via a central or peripheral vein.

In the co-administration cycles, bosentan will be administered orally twice daily in the morning and evening during the prior five consecutive days, self-administered at home from Day -5 to Day -1 (i.e., five days before lurbinecetin infusion), and once daily on Day 1 (i.e., the day of lurbinecetin infusion), following recommendations at the Summary of Product Characteristics (SmPC). On Day 1 (i.e., the day of lurbinecetin infusion), bosentan will be given immediately prior to starting the lurbinecetin infusion. In fact, bosentan should be administered after obtaining the bosentan PK sample #1 and before the start of lurbinecetin infusion (-15 min to -1 min).

In case of lurbinecetin delay (≤ 2 days), bosentan could be administered twice daily during a maximum of seven consecutive days before lurbinecetin infusion, and supplied at the study center once daily on Day 1 (before lurbinecetin infusion).

All patients will receive a maximum of three cycles: two consecutive cycles of lurbinecetin, one cycle with and one cycle without bosentan co-administration (in different order depending on the study Sequence 1 or Sequence 2 of treatment), followed by a third cycle with lurbinecetin alone (this last optional for patients with clinical benefit).

Patients will be randomized in a 1:1 ratio to Sequence 1 (TR: Test- Reference; lurbinecetin + bosentan in Cycle 1) or Sequence 2 (RT: Reference-Test; lurbinecetin + bosentan in Cycle 2). Lurbinecetin will be administered as a 1-hour (-5/+20 min) intravenous (i.v.) infusion q3wk via a central or peripheral vein. The dose of lurbinecetin will be 3.2 mg/m² for all patients when administered with and without bosentan. If toxicity occurs, the appropriate intra-patient dose level (DL) reductions will be implemented in the subsequent cycle.

The enrollment of the patients will be simultaneous. However, if once the first three patients enrolled have completed Cycle 1 and Cycle 2, total lorbinecetin exposure does not allow an adequate PK assessment and if no unacceptable or life-threatening toxicities have occurred, the dose of lorbinecetin to be co-administered with bosentan in the remaining five patients can be adjusted accordingly.

This decision will be made by the Sponsor and the study Investigators. Therefore, the planned dose of lorbinecetin, when given with bosentan for the remaining five patients, will be based on the acceptability of the PK and safety results from the first three patients. If the initial three patients do not experience adverse events (AEs) which might require a dose-reduction, the dose of lorbinecetin may still be adjusted (based on the assumption of dose-proportional pharmacokinetics) to produce plasma lorbinecetin area under the curve (AUC) values that are comparable to those when lorbinecetin is given in the absence of bosentan. However, if toxicity occurs in the initial three patients, the appropriate dose-reduction of lorbinecetin will be implemented in the remaining five patients accordingly.

Patients will receive lorbinecetin until disease progression, unacceptable toxicity, consent withdrawal or while it is considered to be in their best interest, and for a maximum of three cycles. Treatment with lorbinecetin outside this study could be continued under a Compassionate Use Agreement after the completion of the optional third study cycle.

All patients will be randomly assigned to the corresponding sequences:

- Sequence 1 (TR):
 - Cycle 1: Bosentan + lorbinecetin
 - Cycle 2: Lorbinecetin alone
 - Cycle 3: Lorbinecetin alone (optional)

- Sequence 2 (RT):
 - Cycle 1: Lorbinecetin alone
 - Cycle 2: Bosentan + lorbinecetin
 - Cycle 3: Lorbinecetin alone (optional)

Lorbinecetin will be administered to eight evaluable patients and for a maximum of three cycles, while considered to be on the patient's best interest or until progressive disease (PD), unacceptable toxicity, intercurrent illness of sufficient magnitude to preclude safe continuation of the study, patient's refusal and/or non-compliance with study requirements, a protocol deviation with an effect on the risk/benefit ratio of the clinical study or any other reason at the physician's judgment that precludes lorbinecetin continuation.

If the patient responds to treatment after the first two cycles according to Investigator criteria for clinical benefit, treatment with lorbinecetin may continue outside this study under a Compassionate Use Agreement at the same dose based on Investigator's decision and upon agreement with the Sponsor. Then, the treating center must request authorization to the relevant Health Authorities and notify the Sponsor in due time. In order to avoid a treatment discontinuation, during the Compassionate Use Agreement authorization an additional third cycle with lorbinecetin is allowed.

All AEs will be graded according to the National Cancer Institute Common Terminology Criteria for Adverse Events (NCI-CTCAE) v.5. Treatment delays, dose reduction requirements and reasons for treatment discontinuation will be monitored throughout the study. The safety profile of patients will be monitored throughout the treatment and up to 31 days (± 10 days) after the last lorbinecetin infusion (end of treatment, EOT), until the patient starts a new antitumor therapy or until the date of death, whichever occurs first. Any treatment-emergent AEs will be followed until recovery to at least grade 1 or stabilization of symptoms or until the start of a new antitumor therapy, until the continuation of treatment outside this study under a Compassionate Use Agreement or death, whichever occurs first. After treatment discontinuation, patients will be followed until resolution or stabilization of all toxicities, if any.

Patients will be evaluated at scheduled visits on three study periods: pre-treatment (screening), treatment (one cycle of lorbinecetin in combination with bosentan and two as a single agent and the third cycle optional) and follow-up of adverse events if any.

3 PATIENTS EVALUABILITY CRITERIA

Patients must fulfill all the inclusion/exclusion criteria to be enrolled in the study.

The study will include the following analysis population set definitions:

- The enrolled population is defined as all patients recorded in the database who have been included in the trial and randomized, regardless of whether they have received the study drug or not. Screening failure patients will not be considered as part of this population.
- The PK population will include all patients who have provided sufficient and interpretable PK parameters to calculate the non-compartmental PK parameters. Evaluable patients should have received the first two complete cycles regardless dose delays or reductions.
- The safety population will include all patients who received at least one dose of lorbinecetin. Patients who have received at least one dose of bosentan but who did not receive any dose of lorbinecetin will be excluded from the safety population and will be performed separately by narratives. The safety population will be used for all safety evaluations.

4 OBJECTIVES AND ENDPOINTS

4.1 *Objectives*

This clinical pharmacology study is designed to assess the impact of bosentan co-administration on lorbinecetin PK parameters administered alone.

4.1.1 *Primary Objective*

- To assess the effect of bosentan on lorbinecetin total plasma exposure in patients with advanced solid tumors.

4.1.2 *Secondary Objective*

- To assess the effect of bosentan on lorbinecetin unbound plasma exposure.
- To assess the effect of bosentan on lorbinecetin major metabolites (i.e., M1 and M4).
- To assess the effect of bosentan on the safety profile of lorbinecetin.
- To collect and store a blood sample for germline DNA extraction for future pharmacogenetic (PGt) analysis of variations on genes that may influence exposure and response (i.e., disposition, metabolism and safety) to lorbinecetin.

4.2 *Endpoints*

4.2.1 *Primary Endpoint*

- Plasma dose-normalized C_{max} and $AUC_{0-\infty}$ of lorbinecetin will be compared between Cycle 1 and Cycle 2. Pharmacokinetic analyses will be evaluated in plasma by standard non-compartmental methods, or population methods, if necessary.

4.2.2 *Secondary Endpoint*

- Differences in dose-normalized total AUC_{0-t} and C_{max} and in Cl , Volume of Distribution at Steady State (V_{ss}) and $T_{1/2}$ of lorbinecetin between Cycle 1 and Cycle 2 will be explored.
- Differences in dose-normalized unbound $AUC_{u,0-\infty}$, $AUC_{u,0-t}$ and $C_{u,max}$ and in CL_u , $V_{ss,u}$ and $T_{1/2,u}$ of lorbinecetin between Cycle 1 and Cycle 2 will be explored.
- Differences in ratios between total $AUC_{0-\infty}$, AUC_{0-t} and C_{max} , of main lorbinecetin metabolites relative to parent drug between Cycle 1 and Cycle 2 will be explored. Additional PK parameters will be calculated if deemed appropriate.
- Treatment safety, including AEs, serious adverse events (SAEs) and laboratory abnormalities will be graded according to the NCI-CTCAE v.5. Additionally, treatment compliance, in particular dose reductions requirements and/or treatment delays due to AEs, and reasons for treatment discontinuation will also be described. Patients will be evaluable for safety if they have received at least one partial or complete infusion of lorbinecetin.

- The presence or absence of pharmacogenetic (PGt) polymorphisms in genes relevant for lorbinecetin disposition (distribution, metabolism and excretion) from a single blood sample collected (only if written IC given) at any time during the trial (but preferably at the same time as the pre-treatments PK sample on Day 1 of Cycle 1), which will be stored to explain individual variability in main PK parameters in future analyses.

5 SAMPLE CONSIDERATIONS

5.1 *Randomization*

A block randomization (1:1 ratio) will be performed to avoid bias in the assignment of patients to treatment sequence group, to increase the likelihood that known and unknown subject attributes (e.g., demographic and baseline characteristics) are evenly balanced across treatment sequence groups, and to enhance the validity of statistical comparisons across treatment sequence groups.

At least eight patients are expected to complete all study procedures, including the collection of sufficient and interpretable PK assessments. Although at least eight patients will be enrolled in this study; it is estimated that complete data from eight patients will be sufficient to estimate the drug-drug interaction of bosentan on the PK of lorbinecetin.

Randomization will apply for all patients.

Patients must be replaced if they are not evaluable for the assessment of the primary endpoint (e.g., if they have not sufficient and interpretable PK parameters).

Randomization will be implemented in Medidata Rave RTSM. A randomization list will be generated to randomly allocate patients to Sequence 1 (TR: Test- Reference; lorbinecetin + bosentan in Cycle 1) or Sequence 2 (RT: Reference-Test; lorbinecetin + bosentan in Cycle 2). Additional randomization lists will be generated in case non-evaluable patients need to be replaced. Variable block sizes and allocation ratios will be used depending on the number of patients to be replaced in each case scenario in order to complete both sequence treatment groups while keeping balance across them. In order to achieve reproducible results, the seed used in the generation of each randomization list will be saved.

5.2 *Sample Size*

This study was designed to assess the potential effects of bosentan on the PK of lorbinecetin in patients with advanced malignancies. The 90% confidence interval (CI) will be used to help with the interpretation of the results. A sample size of eight patients was based on feasibility and clinical considerations. Based on previous studies, the intra-subject coefficient of variation (CV) of lorbinecetin PK parameters is estimated to be more than 30%. The precision (half-width) of the 90% CI for [(lorbinecetin + bosentan) / lorbinecetin alone] comparison on the log-scale will extend 0.389 from the observed differences in means, assuming that the intra-subject CV around 40%. This half-width corresponds to a 90% CI in the range of 70% and 147% assuming the ratio of the means equal to unity for each PK parameter. This 90% CI will be used to help with the interpretation of the results.

6 STATISTICAL METHODOLOGY

The PK definitions and analysis plan will be described by the Clinical Pharmacology department in a separate document. The present Statistical Analysis Plan (SAP) is focused on the statistical methodology for safety.

Safety analyses will consider treatment emergent AEs and SAEs, according to their relationship with study treatment, as well as analytical results, deaths and the reasons for treatment discontinuations, delays and/or dose reductions.

All AEs and SAEs will be coded using the Medical Dictionary for Regulatory Activities (MedDRA).

Descriptive statistics will be used to characterize the profiles of drug-related AEs, drug-related deaths, SAEs, clinical laboratory data, drug-related delays and/or treatment discontinuations. Tables will be displayed by sequence and treatment (Sequence 1 [TR] vs. Sequence 2 [RT]) and treatment group (Test [lurbinectedin administered in combination with bosentan] vs. Reference [lurbinectedin alone]) .

6.1 Toxicity and Adverse Events

The toxicity evaluation will be graded according to National Cancer Institute Common Terminology Criteria for Adverse Events (NCI-CTCAE v.5).

Summary of overall AEs will be done by system organ class (SOC) and preferred term (PT), by severity (worst toxicity grade) and by relationship to the study drug (any of them or both). Tables will be sorted by category of events using SOC and PT.

6.2 Clinical Laboratory Evaluation

Laboratory results will be classified according to the NCI-CTCAE v.5.

All laboratory visits reported as “End of treatment” visit will be mapped to the last cycle visit for each patient. Worst grade per patient and per cycle for applicable values during treatment will be shown.

The following hematological values will be displayed: hemoglobin, erythrocytes (RBC), white blood cells count (WBC), neutrophils, lymphocytes, monocytes, hematocrit and platelets count.

For the analysis by sequence, overall cross tabulation will be presented for the worst grade during treatment vs. the baseline toxicity grading of anemia, lymphopenia, neutropenia, leukopenia and thrombocytopenia.

If a grade ≥ 3 neutropenia or thrombocytopenia occurs during a treatment cycle, the first day it reaches grade 3 or 4 (counting from the start of the cycle) and the duration of the abnormality (i.e., until recovery to grade ≤ 2) will be tabulated. The information will be shown by means of median and range.

The following biochemical and coagulation values will be displayed: aspartate aminotransferase (AST), alanine aminotransferase (ALT), Alkaline Phosphatase, lactate dehydrogenase (LDH), creatinine, creatinine clearance, glucose, creatine phosphokinase (CPK), CPK-MB fraction, gamma glutamyltransferase (GGT), total bilirubin, direct bilirubin, serum electrolytes (Na⁺, K⁺, Mg⁺⁺), total calcium, total proteins, albumin, C-reactive protein count (CRP) and the international normalized ratio (INR).

If a grade ≥ 3 AST or ALT increase occurs during a treatment cycle, both the day it peaked and the duration of the abnormality will be tabulated. The information will be shown by means of median and range.

Overall cross tabulation will be presented for the worst grade during treatment vs. the baseline toxicity grading of biochemical abnormalities.

6.3 Physical Examination, Vital signs, Left Ventricular Ejection Fraction and Electrocardiogram Findings

Tables summarizing the performance status (PS), height, body weight and body surface area (BSA), vital signs, left ventricular ejection fraction (LVEF) at baseline and during the treatment will be prepared.

If appropriate, changes in the ECOG PS and body weight of each patient during the treatment compared with baseline will also be done.

Cardiac rhythm will be done in triplicate and identified ECG intervals of at least 30 seconds of duration, PR interval and QT interval (raw and corrected by HR using Bazett's formula). Mean of all ECGs collected on each time point will be used for analysis.

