STUDY OBJECTIVES	
Primary:
 
 • To assess the effect of bosentan on lurbinectedin total plasma exposure in patients with advanced solid tumors. 
Secondary:
 
 • To assess the effect of bosentan on lurbinectedin unbound plasma exposure. • To assess the effect of bosentan on lurbinectedin major metabolites (i.e., M1 and M4). • To assess the effect of bosentan on the safety profile of lurbinectedin. • To collect and store a blood sample for germline DNA extraction for future pharmacogenetic (PGt) analysis of variations on genes that may influence exposure and response (i.e., disposition, metabolism and safety) to lurbinectedin.
STUDY DESIGN	
Prospective, open-label, two-way crossover, phase Ib drug-drug interaction study in patients with advanced solid tumors.
 
The study will include a pre-treatment (screening) phase followed by a treatment phase consisting of two lurbinectedin cycles, one cycle in combination with bosentan and one cycle as single agent (in different order depending on the study sequence), and one additional third cycle of lurbinectedin as a single agent for patients who meet the continuation criteria and obtain a clinical benefit after the first two cycles, and then follow-up of adverse events if any.
 
Patients who meet the continuation criteria and obtain a clinical benefit after the first two cycles according to the Investigator's criteria will have the opportunity to continue treatment under a Compassionate Use Agreement after the completion of the optional third study cycle. Patients will be treated as outpatients. At the discretion of the Investigator, patients may be admitted to the study center on Day -1 or Day 1 and monitored, at least, until completion of the Day 1 pharmacokinetic (PK) blood sample collections.
 
All patients will receive a maximum of three cycles: two consecutive cycles of lurbinectedin, one cycle with and one cycle without

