TREATMENT SCHEDULE AND ADMINISTRATION ROUTE	
Patients will receive lurbinectedin as a 1-hour (-5/+20 min) i.v. infusion on Day 1 every three weeks (q3wk), over a minimum of 100 mL dilution on 5% glucose or 0.9% sodium chloride via a central line (or a minimum of 250 mL dilution if a peripheral line is used). Patients will receive a maximum of three cycles: two consecutive cycles of lurbinectedin, one cycle with and one cycle without bosentan co-administration followed by a third cycle with lurbinectedin alone (this last optional for patients with clinical benefit). In the co-administration cycles, bosentan will be administered orally twice daily in the morning and evening during five consecutive days, self-administered at home from Day -5 to Day -1 (i.e., five days before lurbinectedin infusion), and once daily on Day 1 (i.e., the day of lurbinectedin infusion), following recommendations at the Summary of Product Characteristics (SmPC). On Day 1 (i.e., day of lurbinectedin infusion), bosentan will be given immediately prior to the start of the lurbinectedin infusion. In fact, bosentan should be administered after obtaining the bosentan pharmacokinetic (PK) sample #1 and before the start of lurbinectedin infusion (-15 min to -1 min). In case of lurbinectedin delay (≤ 2 days), bosentan could be administered twice daily during a maximum of seven consecutive days before lurbinectedin infusion, and supplied at the study center once daily on Day 1 (before lurbinectedin infusion). All patients will be randomly assigned to the corresponding sequences: Sequence 1 (TR):
 
 • Cycle 1: Bosentan + lurbinectedin • Cycle 2: Lurbinectedin alone • Cycle 3: Lurbinectedin alone (optional) 															

	
Sequence 2 (RT):
 
 • Cycle 1: Lurbinectedin alone • Cycle 2: Bosentan + lurbinectedin • Cycle 3: Lurbinectedin alone (optional)

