11.4 Clinical Laboratory Evaluation

11.4.1 Hematological Abnormalities

Table 11.4.1.1 Hematological abnormalities: Worst grade per treatment

	BOS+LRB						LRB alone					
	All grades		Gr \geq 3		Gr \geq 4		All grades		Gr \geq 3		Gr \geq 4	
	N	%	N	%	N	%	N	%	N	%	N	%
Anemia												
Leukopenia												
Lymphopenia												
Neutropenia												
Thrombocytopenia												

Notes: Percentage is based on number of patients by treatment, when applicable.

BOS, bosentan; LRB, lirbinezidin.

Listing 11.4.1.2 Hematological abnormalities grade \geq 3

Treatment group [†]	Subject	Event	Grade

[†]BOS+LRB/LRB alone

Listing 11.4.1.3 Hematological tests not assessed by patient

Treatment group [†]	Subject	Lab. test

[†]BOS+LRB/LRB alone

Table 11.4.1.4 Hematological abnormalities: Worst grade per patient

	S1 (TR)			S2 (RT)			Total					
	All grades		Gr \geq 3	Gr \geq 4	All grades		Gr \geq 3	Gr \geq 4	All grades		Gr \geq 3	Gr \geq 4
	N	%	N	%	N	%	N	%	N	%	N	%
Anemia												
Leukopenia												
Lymphopenia												
Neutropenia												
Thrombocytopenia												

Notes: Percentage is based on number of patients in total and by sequence, when applicable.

S1, Sequence 1; S2, Sequence 2; TR, test-reference; RT, reference-test.

Listing 11.4.1.5 Hematological abnormalities by cycle grade \geq 3

Sequence	Subject	Event	Cycle	Grade

Listing 11.4.1.6 Hematological tests not assessed by cycle

Sequence	Subject	Cycle	Lab. test

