11.5 Linear Mixed-effects Model

If applicable, to compare the incidence of grade ≥ 4 or grade ≥ 3 between the combination and lurbinectedin alone, a generalized linear mixed-effects model will be fit to the data with treatment (Combination or lurbinectedin alone), period and sequence as fixed effects, and patients nested in sequences as a random effect.

Table 11.5.1.1 Safety comparison between combination and lurbinectedin alone[†]

	Combination	Lurbinectedin alone	p-value [‡]
Any grade ≥ 3 AE			
Any grade ≥ 4 AE			
Any grade ≥ 3 treatment-related AE			
Any grade ≥ 4 treatment-related AE			
Any abnormality (G ≥ 3) in laboratory value (hema, bio)			
Any abnormality (G ≥ 4) in laboratory value (hema, bio)			

[†] A generalized mixed-effects model will be fit for each safety evaluation

[‡] p-values will be provided for the comparison between treatments (combination vs. Lurbinectedin alone) or including the sequence effect if deemed necessary.

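### End-of-treatment laboratory results go to the last cycle and Cycle 3 is not excluded, so the two treatments can be compared on unequal numbers of laboratory results

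*SAP*

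**What the plan says.** **Assignment of EOT results.** SAP 6.2 (Clinical Laboratory Evaluation) says that each EOT laboratory "visit will be mapped to the last cycle visit for each patient". It adds: "Worst grade per patient and per cycle for applicable values during treatment will be shown".

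**Comparison by treatment.** SAP Table 11.4.1.1, "Hematological abnormalities: Worst grade per treatment", sets bosentan plus lurbinectedin beside lurbinectedin alone. Table 11.4.2.1 does the same for biochemistry, and Tables 11.4.3.2 and 11.4.3.4 give time courses by treatment. SAP 11.5 plans, if applicable, a generalized linear mixed model with a p-value for rows such as "Any abnormality (G ≥ 3) in laboratory value (hema, bio"). None of these outputs is limited to Cycles 1 and 2.

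**Which treatment is last.** In the Protocol Synopsis, Sequence 2 (RT) has "Cycle 2: Bosentan + lurbinectedin", while Sequence 1 (TR) has lurbinectedin alone in Cycle 2. Both may add "one additional third cycle of lurbinectedin as a single agent for patients who meet the continuation criteria" and who obtain a clinical benefit.

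**Timing.** Protocol 5.2 puts EOT at 31 (±10) days after the last lurbinectedin dose.

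**The concern.** The treatment label of an EOT result depends on the patient's sequence and on how many cycles the patient received. Because Cycle 3 is always lurbinectedin alone, an RT patient who takes it moves the EOT result from Test to Reference. Cycle 3 also adds its own Day 1 result to Reference.

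A worst grade can stay the same or rise as results are added; it cannot fall. If Reference has more results, and later ones, the comparison can tilt towards more abnormalities on lurbinectedin alone for reasons unrelated to bosentan. Whether Cycle 3 is taken depends on clinical benefit and the continuation criteria, so randomization does not balance it.

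The stake is a secondary objective, the effect of bosentan on the safety profile. With eight patients, one reclassified patient changes a percentage by 1/8 = 12.5 points.

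**Working it through.** The plan gives no figure on this point to reproduce. The check is a count of scheduled laboratory sets by treatment.

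**Inputs**
- Eight patients randomized 1:1, so four TR and four RT (Protocol Synopsis).
- Hematology and Biochemistry A: Days 8 and 15 of Cycle 1; Days 1, 8 and 15 of Cycle 2; Day 1 only of Cycle 3 (Protocol 6.4, Table 5); and EOT (Protocol 6.5).
- Biochemistry B: Day 1 of Cycles 2 and 3, always before the infusion, and EOT. There is no Day 8 or Day 15 test.

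**Assumptions**
- All eight complete two cycles without delay.
- k1 TR and k2 RT patients take Cycle 3. The documents give no expected uptake, so each ranges from 0 to 4.
- A Day 1 set counts to the cycle it opens.
- The conditional Cycle 1 Day 1 repeat is left out.

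**Formulas, hematology and Biochemistry A**
- Day 8/15 sets: 8 patients × 2 = 16 for each treatment, whatever k1 and k2 are.
- Cycle 2 Day 1 sets: 4 for each treatment.
- Cycle 3 Day 1 sets: k1 + k2, all to Reference.
- EOT sets: Reference 4 + k2; Test 4 − k2.
- Totals: Reference = 16 + 4 + (k1 + k2) + (4 + k2) = 24 + k1 + 2·k2; Test = 16 + 4 + (4 − k2) = 24 − k2.

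| k1 (TR) | k2 (RT) | EOT, Reference vs Test | Total sets, Reference vs Test |
|---|---|---|---|
| 0 | 0 | 4 vs 4 | 24 vs 24 |
| 4 | 0 | 4 vs 4 | 28 vs 24 |
| 2 | 2 | 6 vs 2 | 30 vs 22 |
| 0 | 4 | 8 vs 0 | 32 vs 20 |
| 4 | 4 | 8 vs 0 | 36 vs 20 |

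The excess for Reference is k1 + 3·k2. Of this, k1 + k2 is the Cycle 3 Day 1 result and 2·k2 is the EOT result changing sides. If all eight take Cycle 3, the excess is 16, made up of 8 + 8.

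**Early stoppers.** Add one treated patient who stops after Cycle 1, with nobody taking Cycle 3. If that patient is TR, EOT is Reference 4 vs Test 5 and the totals are 24 vs 27. If RT, EOT is 5 vs 4 and the totals are 27 vs 24. Protocol 5.3 keeps replaced patients who were treated in the safety analysis.

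**Biochemistry B.** Under the counting assumption above, the only scheduled result after dosing that is labelled with either treatment is the EOT one, so its split is the EOT column. Nine Table 11.4.2.1 rows rest on it: hypoalbuminemia, and the high and low rows for sodium, potassium, magnesium and calcium.

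**The case against.** The other side has a substantial case, and most of it limits the size of the point.

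- **The direction is not fixed.** A reader might infer that the EOT rule always gives lurbinectedin alone more and later results, and so makes the combination look safer. The documents do not support that. With no Cycle 3 the split is 4 vs 4, and a TR patient who stops after Cycle 1 tips it towards Test. No effect on any grade ≥3 count has been shown; only results have been counted.
- **The mapping alone is not the cause.** A reader might infer that excluding Cycle 3 would not help. If Cycle 3 is dropped together with its EOT result, the EOT sets are Reference 4 − k1 and Test 4 − k2, which are equal whenever uptake is equal. The later last-cycle result then belongs to Period 2, and the 11.5 model already contains period and sequence.
- **Observation time.** A reader might set the latest EOT day, 41, against a 21-day cycle. That compares a maximum with a nominal length. Protocol 7.4 allows delays of up to 14 days, so a cycle that is not the last can run to 21 + 14 = 35 days.
- **Neutropenia.** The nadir is in the middle of the second week (SAP 1), and Day 8/15 sets are 16 vs 16 throughout.
- **Visibility.** Grade ≥3 abnormalities are listed by cycle (Listings 11.4.1.5 and 11.4.2.5) and laboratory values by date (Listings 13.19 and 13.21). The comparison is secondary and mainly descriptive.

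All of this stands. It does not remove the gap: the by-treatment outputs do not say how Cycle 3 and its EOT result are handled, and the stated rule yields unequal counts once Cycle 3 is used. Listings let a reader find late values but do not correct a table or a p-value.

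**Conclusion.** The point holds in conditional form, as a low-cost improvement. Pooling Cycle 3 into lurbinectedin alone, together with the EOT mapping, makes the by-treatment laboratory comparison unequal. Among eight two-cycle completers the EOT split runs from 4 vs 4 to 8 vs 0. Scheduled hematology and Biochemistry A sets run from 24 vs 24 to 36 vs 20 (Reference vs Test).

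Among such patients any imbalance favours more data for Reference. Its size depends on Cycle 3 uptake, which the documents do not predict, and early stoppers can reverse it. The likely effect on neutropenia is small. Biochemistry B, and the rows of Table 11.5.1.1 that pool hematology with biochemistry, are more exposed. The counts assume scheduled visits only, no delays and four patients per sequence. The primary pharmacokinetic comparison is not touched.

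**What to change.** Add one rule to SAP 6.2, covering Tables 11.4.1.1, 11.4.2.1, 11.4.3.2 and 11.4.3.4 and the laboratory rows of Table 11.5.1.1:

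- Use Cycles 1 and 2 only, with the same window in both: from after the Day 1 infusion through 21 days after that infusion. Count the next cycle's pre-dose Day 1 sample to the preceding cycle if it falls in the window.
- Show EOT and other Cycle 3 results in separate columns, and keep them in the listings and the by-sequence overall tables.
- For Biochemistry B, state that the last cycle may have no result in the window, and show EOT separately.

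Visits belonging to Cycles 1 and 2 then give 16 + 4 = 20 scheduled hematology and Biochemistry A sets for each treatment, whatever the Cycle 3 uptake. Counting the Cycle 3 pre-dose sample back to Cycle 2 adds k1 to Reference and k2 to Test. That is equal under equal uptake and differs by at most 4, against a gap of up to 16 now.

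The cost is a short addition to the SAP and a date filter in the programs. The downside is that late results, and those from delayed cycles, leave the by-treatment comparison, though they remain reported elsewhere. No visit or sample changes.
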